4.2.11 Safety

Safety data will be summarised and listed only. No formal statistical analyses will be performed on the safety data. All safety data will be summarised by actual treatment group (olaparib or placebo) including patients who have dose reduction for blinded period of study. Any patient who received an initial dose of olaparib will be included in the olaparib group, even if the patient was planned to receive placebo. Similarly, any patient who received an initial dose of placebo will be included in the placebo group, even if the patient was planned

to receive olaparib. However, some listings such as AEs listings will display the actual dose the patient received at onset of an AE.

Adverse events

All AEs, both in terms of Medical Dictionary for Regulatory Activities (MedDRA) preferred term and Common Toxicity Criteria for Adverse Events (CTCAE) grade, will be listed and summarised descriptively by count (n) and percentage (%) for each treatment arm. MedDRA dictionary will be used for coding. Any AE occurring before olaparib/placebo treatment (i.e. before Study Day 1) will be included in the AE listings, but will not be included in the summary tables (unless otherwise stated). These will be referred to as 'pre-treatment'.

The summary tables will include all AEs that occurred after the start of treatment up until the end of the 30 day follow-up period. The 30 day follow-up period will be defined as 30 days following discontinuation of olaparib/placebo treatment.

All reported AEs will be listed along with the date of onset, date of resolution (if AE is resolved), investigator's assessment of severity and relationship to study drug. Frequencies and percentages of patients reporting each preferred term will be presented (i.e. multiple events per patient will not be accounted for apart from on the episode level summaries).

Partially missing dates will be imputed as per the phUSE guidelines (http://www.phusewiki.org/wiki/index.php?title=Imputing Partial Dates)

For date of onset:

- Missing day Impute the 1st of the month unless month is same as month of first dose of study drug then impute first dose date
- Missing day and month impute 1st January unless year is the same as first dose date then impute first dose date
- Completely missing impute first dose date unless the end date suggests it could have started prior to this in which case impute the 1st January of the same year as the end date.

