When imputing a start date ensures that the new imputed date is sensible i.e. is prior to the end date of the AE.

For date of resolution:

- Missing day Impute the last day of the month unless month is same as month of first dose of study drug then impute last dose date
- Missing day and month impute 31st December unless year is the same as first dose date then impute last dose date

Date 15 February 2022

• Completely Missing – need to look at whether the AE is still ongoing before imputing a date and also when it started in relation to study drug. If the ongoing flag is missing then assume that AE is still present (i.e. do not impute a date). If the AE has stopped and start date is prior to first dose date then impute the 1st dose date, if it started on or after first dose date then impute a date that is after the last dose date.

Summary information (the number and percent of patients by treatment) will be tabulated for:

- All AEs
- All AEs causally related to study medication
- AEs with CTCAE grade 3 or higher
- AEs with CTCAE grade 3 or higher, causally related to study medication
- AEs with outcome of death
- AEs with outcome of death causally related to study medication
- All serious adverse events (SAEs)
- All SAEs causally related to study medication
- AEs leading to discontinuation of olaparib/placebo
- AEs leading to discontinuation of olaparib/placebo, causally related to olaparib/placebo
- Other significant AEs
- Other significant AEs causally related to olaparib/placebo

An overall summary of the number and percentage of patients in each category will be presented, as will an overall summary of the number of episodes in each category. In addition, a truncated AE table of most common AEs, showing all events that occur in at least 5% of patients overall will be summarised by preferred term, by decreasing frequency. This cut-off may be modified after review of the data.

Each AE event rate (per 1000 patient years) will also be summarised by preferred term within each system organ class. For each preferred term, the event rate will be presented and will be defined as the number of patients with that AE divided by the sum of the duration from the start of treatment to 30 days after the last treatment dose (for patients without the event) and the time to the AE (for patients with the event) in each group multiplied by 1000.

Date 15 February 2022

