For each AE, median time to first onset of the AE will be presented in patients in the safety analysis set by actual treatment group. Patients who did not experience the AE will not be included in the summaries. Summary tables of time to first onset for each AE will also be produced (e.g. 1-28 days, 29-56 days, 57-84 days, 85-112 days, >112 days). Median duration of the AE will be presented in patients who experienced each AE.

Laboratory assessments

Box-plots of absolute values and change from baseline for a selection of continuous laboratory assessments will be presented.

For all continuous laboratory assessments, absolute value, change from baseline and percentage change from baseline will be summarised using descriptive statistics at each scheduled assessment time by actual treatment group. For categorical laboratory assessments, shift from baseline will be summarised using frequency and proportion at each scheduled assessment time by actual treatment group.

Shift tables for laboratory values by worst common toxicity criteria (CTC) grade will be produced, and for specific parameters separate shift tables indicating hyper- and hypodirectionality of change will be produced. For parameters with no CTCAE grading, shift tables from baseline to worst value on-treatment will be provided (i.e. on-treatment is defined as data collected up until 30 days after the last dose of olaparib/placebo).

A scatter plot of ALT versus total bilirubin, both expressed as multiples of ULN, will be produced. The scatter plot will be repeated for AST versus total bilirubin.

Liver biochemistry test results over time for patients with elevated ALT or AST, and elevated total bilirubin (at any time) will be plotted. Individual patient data where ALT or AST plus total bilirubin are elevated at any time will be listed also.

Urinalysis results (categorical data collected at baseline and only if clinically indicated post-baseline) will be listed only.

Clinically significant laboratory results will be flagged and listed. Reference ranges will also be listed. All laboratory summaries and listings will be presented by actual treatment group.

ECGs

ECG data will be listed by actual treatment group.

Vital signs

Vital signs (SBP, DBP, pulse rate, body temperature and weight) will be summarised over time in terms of absolute values and changes from baseline at each scheduled measurement by actual treatment group. Vital signs data will be listed by actual treatment group.

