Age will be derived as age at last birthday in whole years using the date of randomisation and date of birth. Where a partial date of birth has been collected, the following imputation rules will be applied in order to calculate the patient's age for use in listings and summaries tables presenting age and/or age group and subgroup analyses based on age:

- If only the month and year of birth has been collected, the day of birth will be imputed as 15th
- If only the year of birth has been collected the day and month of birth will be imputed as 1st July
- If the date of birth is completely missing, the derived age of the patient will also be missing.

Date of birth will be listed as it has been collected on the eCRF.

Overall disease classification will be categorised as follows:

- If a patient has any site of metastic disease, they are classified as 'Metastatic',
- If a patient has no sites of metastatic disease and does have sites of local disease they are classified as 'local'
- Else if they have no sites of disease identified and no target lesions present at baseline and no non-target lesions present at baseline (as assessed by the investigator) and they do have a valid investigator assessed baseline scan, they are classified as 'NED',
- Else classified as 'unknown'

Partial dates for start and end of concomitant medications will be derived as per date of onset and date of resolution for adverse events, respectively.

Patients who were unblinded (a) prior to disease progression and (b) prior to or on the day of treatment discontinuation will be listed.

A listing containing both the eCRF BRCA results and the Myriad gBRCA and Foundation Medicine tBRCA results will be produced.

Patients disposition data will also be summarised and listed at the time of each planned OS analysis.

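### The partial-date rule for AE resolution tests the month or year of first dose but imputes the last dose date, which can fall outside the recorded month or year (minor)

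*SAP*

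**What the plan says.** SAP 4.2.11 (Safety) gives separate rules for partial onset dates and partial resolution dates of AEs, and names an external guideline as their source.

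- Onset, day missing: "Impute the 1st of the month unless month is same as month of first dose of study drug then impute first dose date". The rule for a missing day and month likewise pairs the year of first dose with the first dose date.
- Resolution, day missing: "Impute the last day of the month unless month is same as month of first dose of study drug then impute last dose date".
- Resolution, day and month missing: "impute 31st December unless year is the same as first dose date then impute last dose date".
- Plausibility check: "When imputing a start date ensures that the new imputed date is sensible i.e. is prior to the end date of the AE". There is no matching check for end dates.

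Under the summary of long-term tolerability in the same section, "Median duration of the AE will be presented in patients who experienced each AE". SAP 4.2.12 reuses the rules: "Partial dates for start and end of concomitant medications will be derived as per date of onset and date of resolution for adverse events".

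**The concern.** In the onset rule the condition and the imputed value belong together: if the AE began in the first-dose month, take the first dose date. The resolution rule keeps the first-dose condition but changes the value to the last dose date. The two agree only when first and last dose fall in the same month (or year). For anyone treated longer, the imputed end date lies outside the month or year that the site recorded.

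This cannot be defended as a conservative convention. The latest end date compatible with the record is already the last day of the recorded month, or 31 December of the recorded year. The exception goes beyond that.

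Three outputs are exposed: AE durations, listings or derived dates that carry imputed end dates, and concomitant-medication end dates. A drug stopped in the first-dose month, with the day missing, would appear to have been taken until last dose.

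**Working it through.** The plan gives no figure for AE duration, so there is nothing of its own to reproduce.

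**Single record (exact, invented dates).** Duration = end date − onset date + 1. First dose is 10 January 2014 and onset 12 January 2014.

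| Recorded end | Last dose | As printed | Latest date the record allows |
|---|---|---|---|
| January 2014 | 10 Apr 2014 | 89 days | 20 days (31 Jan) |
| January 2014 | 10 Jul 2014 | 180 | 20 |
| January 2014 | 9 Jan 2015 | 363 | 20 |
| January 2014 | 9 Jan 2016 | 728 | 20 |
| 2014 only | 9 Jan 2016 | 728 | 354 (31 Dec) |

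The last-dose dates follow the planned treatment period of up to two years (Protocol 5.5.2.1).

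**A negative duration is also possible.** Take first dose 2 January, last dose 10 January, onset 15 January (inside the 30-day AE window), and end recorded as January. The printed rule gives 10 − 15 + 1 = −4 days. Replacing first dose by last dose does not cure this case, because January is also the month of last dose. An explicit bound at onset is therefore needed.

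**Effect on a median (simulation).** The documents do not say how often end dates are partial, so every input here is an assumption:

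- first dose uniform from September 2013 to February 2015;
- onset exponential, mean 7 days after first dose;
- duration exponential, median 7, 14 or 30 days;
- last dose uniform at 3 to 24 months;
- end day missing at random in 2%, 5%, 10% or 20% of AEs.

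The AE then ends in the first-dose month in 51%, 35% and 20% of cases respectively.

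| True median | Printed rule, 2/5/10/20% missing | Corrected rule |
|---|---|---|
| 7 days | 8/8/9/10 | 8/8/8/10 |
| 14 days | 15/16/17/20 | 15/15/16/18 |
| 30 days | 31/32/34/38 | 31/31/32/34 |

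The difference is 0 to 2 days except in the most extreme cell (30-day AE, 20% missing), where it is 38 − 34 = 4 days. A second calculation, with onset spread evenly over the first 28 days and only first-month end dates imputed, gave smaller shifts at 20% missing: 16.3 against 15.5 days for a true median of about 15, and 62.6 against 60.6 for about 61.

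**Rows with few patients.** Suppose a row of n patients does contain one affected record (14-day AE, same assumptions).

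| n | Printed | Corrected |
|---|---|---|
| 1 | 407 | 17 |
| 2 | 214 | 16.5 |
| 3 | 25 | 16 |
| 5 | 20 | 15 |
| 10 | 17 | 15 |
| 20 | 15.5 | 15 |

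These figures are conditional on the bad record being present. With 35% of AEs ending in the first-dose month and 5% of end days missing, the chance of at least one such record is 1 − (1 − 0.35 × 0.05)^n, which is 1.75%, 3.5% and 5.2% for n = 1, 2 and 3.

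**The case against.** The slip is real but its reach is short, and most of the case for that stands.

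- **Common and rare AEs.** The protocol's evidence for early onset concerns nausea and vomiting (5.5.5). In the Phase II study cited there, nausea affected 71% of olaparib patients. Such rows are large, and large rows hardly move. Nothing in the documents says that rare AEs cluster in the first month, so the small-row figures describe what could happen, not what to expect.
- **Which rows are planned.** Duration is planned for each AE, directly after a list of six grouped common AEs. If only those six are meant, small rows largely disappear. The text allows either reading.
- **Data quality.** Visits on Days 8, 15, 22 and 29 with AEs recorded at each (Protocol 3.1 and 6.2.2), source verification (9.3) and queries for missing data (10) make a lost end day in month one less likely than later.
- **The cited guideline.** It is not among the documents, so what was programmed cannot be seen. If it differs from the printed text, the SAP carries two rules, which is itself a reason to correct the text.

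These arguments limit the size of the problem. None makes the printed rule correct.

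**Conclusion.** The rule is wrong as printed, in two places, and nothing in the protocol or SAP corrects it. That rests on the text alone. Severity is minor: the affected output is descriptive, and no test, alpha or efficacy result uses it. The statement that common-AE medians shift by about 0 to 2 days rests on the assumed 2% to 20% of partial dates and the assumed durations.

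Three stronger readings are not supported.

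- A reader might infer that the reported AE durations are unreliable in general. Complete dates need no imputation, and partial dates outside the first-dose month or year are handled sensibly.
- A reader might infer a bias against olaparib, because the error grows with time on treatment. That would need longer treatment on olaparib together with enough affected records. The documents give no partial-date rate in either arm.
- A reader might infer that ongoing AEs have no rule. The SAP leaves their end date blank. How they enter the median is an unstated detail and not part of this point.

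**What to change.** In SAP 4.2.11, change the condition in both resolution rules from first dose to last dose:

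- Day missing: last day of the recorded month, or the last dose date if that is the month and year of last dose.
- Day and month missing: 31 December of the recorded year, or the last dose date if that is the year of last dose.

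Add one sentence: an imputed end date must stay within the recorded month or year, must not precede onset, and must not follow death or data cut-off. Where the last dose date breaks one of these bounds, use the last day of the recorded period, or death or data cut-off if earlier. SAP 4.2.12 refers back to these rules, so concomitant medications need no separate edit.

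The cost is two words, one added sentence and a re-run of the date derivation, with no new data. It remains useful for the selected safety summaries repeated at each planned OS analysis, if AE duration is among them.

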4.2.12 Demographic and baseline characteristics data

The following will be listed and summarised by randomised treatment group:

- Patient disposition (including screening failures and reason for screening failure)
 This will also include the number (%) of patients who at two years had no evidence of disease and so discontinued study treatment
- Important deviations
- Inclusion in analysis populations
- Demographics (age, age group, sex, race and ethnicity)
- Patient characteristics at baseline (height, weight, weight group (<65, 65-90, > 90), body mass index (BMI) and body mass index group ('Normal (<25)', 'Overweight (25-30)' and 'Obesity (>30)')
- Stratification factors recorded on the eCRF
- Stratification factors according to the randomisation
- Patient recruitment by country and centre

Date 15 February 2022

- Previous ovarian cancer therapy
- Previous therapy for other cancer
- Disease characteristics at baseline (ECOG performance status, *BRCA* gene name at screening [*BRCA1*, *BRCA2* or Both or Missing] confirmed locally and by Myriad, *gBRCA* status confirmed locally and by Myriad testing [*gBRCAm*, *gBRCA wt*, *gBRCA VUS*, Missing], *tBRCA* status confirmed by Foundation Medicine testing [*BRCAm*, *BRCA wt*, *BRCA VUS*, Missing], primary tumour location, histology type, tumour grade, International Federation of Gynecology and Obstetrics (FIGO) stage, time from previous platinum chemotherapy to reandomisation, baseline CA-125 value, On-study baseline tumour biopsy and overall disease classification)
- Extent of disease
- Disease related medical history (including number of regimens of previous platinum chemotherapy)
- Relevant surgical history
- History of debulking surgery
- Number of blood transfusions
- Physical examination at baseline
- Time from completion of first line platinum chemotherapy to randomisation
- Disallowed concomitant medications
- Allowed concomitant medications
- Post-discontinuation cancer therapy
- Radiotherapy (previous, on randomised treatment and post-treatment discontinuation)
- BRCA mutation status (by Local germline and Myriad germline, by Myriad germline and tumour BRCA and by Local germline and tumour BRCA)
- Deleterious and suspected deleterious mutation types in germline and tumour BRCA patients

AZ drug dictionary (AZDD) will be used for concomitant medication coding.

Date 15 February 2022

Age will be derived as age at last birthday in whole years using the date of randomisation and date of birth. Where a partial date of birth has been collected, the following imputation rules will be applied in order to calculate the patient's age for use in listings and summaries tables presenting age and/or age group and subgroup analyses based on age:

- If only the month and year of birth has been collected, the day of birth will be imputed as 15th
- If only the year of birth has been collected the day and month of birth will be imputed as 1st July
- If the date of birth is completely missing, the derived age of the patient will also be missing.

Date of birth will be listed as it has been collected on the eCRF.

Overall disease classification will be categorised as follows:

- If a patient has any site of metastic disease, they are classified as 'Metastatic',
- If a patient has no sites of metastatic disease and does have sites of local disease they are classified as 'local'
- Else if they have no sites of disease identified and no target lesions present at baseline and no non-target lesions present at baseline (as assessed by the investigator) and they do have a valid investigator assessed baseline scan, they are classified as 'NED',
- Else classified as 'unknown'

Partial dates for start and end of concomitant medications will be derived as per date of onset and date of resolution for adverse events, respectively.

Patients who were unblinded (a) prior to disease progression and (b) prior to or on the day of treatment discontinuation will be listed.

A listing containing both the eCRF BRCA results and the Myriad gBRCA and Foundation Medicine tBRCA results will be produced.

Patients disposition data will also be summarised and listed at the time of each planned OS analysis.

4.2.13 Treatment exposure

The following summaries related to study treatment will be produced for the safety analysis set by actual treatment group:

- Total exposure of olaparib/placebo.
- Actual exposure of olaparib/placebo.
- Reasons for dose reductions, dose interruptions, and dose modifications of olaparib/placebo. Dose reductions and dose interruptions will be based on investigator initiated dosing decisions. Dose interruptions due to "Subject Forgot to Take Dose" will be omitted from these summaries.
- Number of dose reductions, dose interruptions, and dose modifications of olaparib/placebo that last for a period of three days or more.
- PID and RDI of olaparib/placebo (entire intended treatment period).

For patients on study treatment at the time of the PFS analysis, the DCO date will be used to calculate exposure.

All treatment information data will be listed for the safety analysis set by actual treatment group.

Selected exposure data will also be summarised and listed at the time of each planned OS analysis.

4.2.14 Data cut-offs

The status of ongoing, withdrawn (from the study) and "lost to follow-up" patients at the time of the PFS analysis (initial OS analysis) and at the time of each planned OS analysis should be obtained by the site personnel by checking the patients notes, hospital records, contacting the patients general practitioner and checking publicly available death registries. In the event that the patient has actively withdrawn consent to the processing of their personal data the vital status of the patient can be obtained by site personnel from publicly available resources where it is possible to do so under applicable local laws.

5 INTERIM ANALYSES

No interim analyses of PFS prior to the primary analysis will be performed; however additional analyses of PFS and/or OS may be performed to meet Regulatory Agency requests. Following the PFS analysis, AstraZeneca agreed to requests from Regulatory Agencies to provide an ad hoc descriptive analysis update to the OS data with a DCO at 5 years after the last patient randomised as part of global enrolment (DCO March 2020).

The first interim analysis for OS will be performed at the time of the PFS analysis. A second interim analysis for OS will be performed when approximately 206 OS events have occurred (approximately 53% maturity of the 391 patients who were randomised in SOLO1). An

Date 15 February 2022

additional descriptive OS analysis will be performed at 7 years post the last patient randomised as part of global enrolment (DCO March 2022).

This study will use an external independent data monitoring committee (IDMC) to perform interim reviews of accumulating study safety data. This committee will be composed of therapeutic area experts and statisticians, who are not employed by AZ, and do not have any major conflict of interest. Following the review the IDMC will recommend whether the study should continue unchanged, be terminated, or be modified in any way. Once the IDMC has reached a recommendation, a report will be provided to AstraZeneca. The report will only include the recommendation and any potential protocol amendments and will not contain any unblinding information.

A separate IDMC charter will be developed which will contain details of the IDMC members and clearly define the responsibilities of the IDMC.

A set of outputs using the data from subjects recruited in Japan will be produced at the time of the primary analysis for Japanese regulatory purposes. The outputs will be repeats of a selection of the main set of outputs and the results will not be described in the clinical study report, but rather will be described in a separate standalone report. In addition, some repeats of output will be produced for subjects recruited in Japan at the last OS timepoint.

